Stress sensitivity and its dysregulation are subject to individual genetic, constitutional and environmental factors (Kreek and Laforge, 2007). These factors impact treatment. Cocaine-dependent patients at baseline, with an abnormal diurnal cortisol secretion profile (48% of the sample), could not become abstinent from cocaine during a lead-in of a clinical trial ([name] et al., 2013, accepted). Therefore, it is reasonable to think that some cocaine-dependent patients - with similar severity of cocaine use - differ in terms of stress sensitivity or dysregulation. Because of this, they may face very different odds of overcoming their addiction. A VP challenge might reveal a form of stress dysregulation related to cocaine use in humans, and provide some answer to this question: Is high stress sensitivity or dysregulation a necessary condition for a positive outcome from OT, from other treatments targeting stress; or could it be applied to anyone with cocaine dependence seeking treatment?]

---

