**Phase 3 involves the repeat to the DDAVP stress challenge and a repeat salivary cortisol collection.**

Table 2 schematizes the structure of the whole protocol.

see uploaded Table 2

---

Week 1, phase 1: In-hospital phase, cocaine-dependent patients.

The purpose of the in-hospital phase is to allow abstinence to begin, and provide an environment amenable to stress sensitivity testing. Patients from either sites can be admitted to the General Research Unit on PI-5 for this phase, during which the following procedures will take place:

1) Establish controlled abstinence.

2) Complete baseline assessments, including Time Line Follow-Back (Litten & Allan, 1992) to quantify drug use, Cocaine Craving Scale (Weiss et al., 1997), Clinician Global Impression-Observer (Guy, 1976), Perceived Stress Scale (Cohen et al., 1983), Hamilton Depression Scale-25 items (Williams, 1988).

3) Upon the 1st negative urine toxicology for cocaine, we will collect baseline salivary cortisol samples at these approximate times: 8-9am, 11-12pm, 2-3pm, 5-6pm.

4) Stress Challenges. These consist of two tests performed on separate days in counterbalanced order, as illustrated below. The test itself will be performed in the Biological Studies Unit. Patients will have breakfast in the morning prior to testing.

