**measurements are repeated at specified time points.**

5) After baseline stress testing is completed, begin randomized administration of intranasal Oxytocin 20 IU per day in the morning, for each remaining day of phase 1. This will serve also as an opportunity to train patients on how to administer intranasal solutions. The steps are as follows: 1) exhale through the nose, head bent forward; 2) while inhaling, spray once into one nostril; 3) repeat step 1 & 2 for the other nostril; 4) repeat steps 1 to 3 again to reach the daily dose of 24 IU of randomized medication. The patients will be instructed by a member of the research staff to ensure proper technique and optimal absorption of the medication. The Oxytocin solution is stable at room temperature for one month after being opened. Nonetheless, the manufacturer recommends that the bottle be kept refrigerated between uses and we will recommend this to the patients as well. Its stability should ensure that transportation to the clinic should not cause degradation, provided it is not exposed to extreme heat (> 100 Fahrenheit), direct sunlight, or frozen.

Phase 1, control participants.

The purpose of Phase 1 for control participants without psychiatric, medical, or addiction disorders is to test their stress sensitivity with the same procedure as cocaine-dependent patients. This is to study if stress dysregulation is more prevalent among cocaine users than normal controls, and to study if vasopressin-based stress mechanisms bear some specificity to the stress dysregulation observed in cocaine-dependent patients.

For control participants, the procedure will be carried out over two days as outpatients. They will be instructed to present themselves between 9 to 10 am on a testing morning, having eaten breakfast. A saline lock will be inserted, and a 2-hour habituation period will follow before testing begins at approximately 1 pm. The procedure will be the same as described for cocaine-dependent patients, and will be administered in counterbalanced order (**see above, stress procedures**). Completion of phase 1 ends their participation in this study.

Phase 1, week 1, cocaine-dependent patients, outpatient version.

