This procedure is based on our previous experience acquired during protocol NYSPI IRB 6013 (mifepristone study for cocaine dependence) with patients who cannot participate in the inpatient procedure. Over a period of 7 days, not counting Saturdays and Sundays, a participant will have to produce at least three consecutive cocaine negative urine toxicologies at daily visits. Once abstinence is established the phase 1 procedures begin (Table 1), with verification of negative toxicology before each testing day. Randomized medication will begin after completion of all the physiological tests.

---

If a urine toxicology test emerges positive for cocaine once Phase-1 procedures have begun, the testing will stop. The patient can then attempt another period of seven days to reach abstinence, complete the baseline testing, and begin randomized medication. If abstinence cannot be reached during this two-week window, the patient will be offered to carry out phase 1 as an inpatient. If the patient cannot participate as an inpatient, referrals to other treatment options will be offered.

Phase 2, outpatient phase, week 2 to 7, cocaine-dependent patients only

During this phase in which only cocaine-dependent patients participate, they will continue randomized medication while participating in a structured program to support and promote continuing abstinence and completion of the study.

For patients continuing at the STARS clinic and DOSA at Waters Place ([name]), the structure of the program during this phase will be as follows:

- 1: Patients continue to receive intranasal Oxytocin (24IU/day) vs. intranasal placebo. During their visits to either clinic, they will administer the randomized medication under supervision from a bottle kept at the clinic. Each witnessed administration will be recorded. Since they "self-administer" the medication, it can be witnessed by any member of the research team.

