8: At one of the visits, the patients will meet with a STARS or DOSA therapist for compliance enhancement therapy aimed at sustaining compliance with participation in all aspects of the study.

9: If a patient misses a visit, every attempt is made to make contact and reschedule as soon as possible. Significant others reported in the locator form may also be contacted if direct contact with the participant cannot be made. The research team continues this effort until contact is made. If a patient cancels a visit, the patient will be instructed to continue the medication with the "at-home" bottle until the next rescheduled visit.

10: Vouchers for completing all procedures of the study (bringing in the bottle, attending all visits, completing all assessments, attending appointments with the therapist and psychiatrist) will be offered (see Compensation section below).

11: At the end of Phase 2 (week 7), patients are rated as responders or non-responders on the end-of-study (EOS) form. To be a responder, frequency or quantity of cocaine use must have decreased by at least 75% compared to the baseline estimate of the 30 days prior to participation in the study. This is estimated by the results of urine toxicology and self-report recorded on the Time-Line-Follow-Back. If the toxicology does not correspond to the self-report, active use of cocaine is recorded. Missed visit will be recorded as days of use. A secondary measure will be time to relapse of cocaine use after completion of the abstinence induction procedure. They also repeat the salivary cortisol collection, and the stress challenge with intranasal desmopressin.

12: Patients are removed from the trial if they miss one week of medication (3 witnessed administration). Patients may elect to stop their participation at any time. Reasons for cessation will be recorded on the end-of-study form. We will attempt to complete end-of-study assessments. Patients may be removed by the investigator under several circumstances: 1) emergence of a medical condition unrelated to the study that would render continued participation

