
3.3 Compensation and data management.

For phase 1, control participants will receive \$150 for their participation; cocaine-dependent patients will receive \$20/day, or will receive \$150 if they complete the whole week. [During phase 2, cocaine-dependent patients accumulate vouchers for completing all study procedures (Bringing home bottle, assessments, study visits).] Each visit with all study procedures completed will earn them \$5. They can also earn \$20 for each week of consecutive and complete participation. Transportation costs are covered (\$5/visit). Total earnings can reach \$450. StudyTrack, a software system for clinical trials will be used for data management.

3.4 Statistical Analysis:

3.4.1. Outcome measures: PHASE 1: **Primary outcomes:** 1) secretion of ACTH (continuous measure of area from the concentration-time curve (AUC) using trapezoid method, pg/mL/min). 2) subjective rating of cocaine craving, stress, depression, anxiety (continuous) 3) difference in ACTH secretion between IN DDAVP (day 1) and IN OT prior to IN DDAVP (day 2) (continuous measure); 4) difference in subjective rating of cocaine

craving, stress, depression, anxiety between IN VP (day 1) and IN OT prior to IN DDAVP (day 2; continuous, controlled for last day of use before entering Phase 1); **PHASE 2: Primary outcome:** 1) maximum number of consecutive abstinent days (continuous measure) ; **Secondary outcome:** 1) cocaine using days (continuous). **Covariates/Predictor Variables:** demographics, age, gender; cocaine data (TLFB, 30 days; IN vs. smoked).

3.4.2. Sample size: In PHASE 1, we will enroll a total of 100 participants: 1) Cocaine group (COC): Cocaine-dependent patients seeking treatment (n=50); 2) Control group (CON): Healthy matched controls (n=50), each matched demographically (see 3.1.1). In PHASE 2, we will randomize the 50 COC patients into two groups: 1) Oxytocin group (OT), n=25; 2) Placebo group (PBO), n=25. An independent statistician will perform, and an independent pharmacist will implement the randomization. Individuals will be stratified by route of cocaine use. The randomization will be balanced in blocks of random size 2 and 4 to prevent compromise of the blind.

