3.4.3. Intent to Treat/ Dropouts and missing data: All primary analysis will be on Intent-to-Treat (ITT) sample, i.e. all subjects from COC and CON groups in Phase 1 (50 per arm) and all subjects randomized to OT and PBO groups in Phase 2 (25 per arm). [In Phase 1, we expect little attrition. Measures as described (3.4.1) will provide usable data after 2 days of measurements. For phase 2, we anticipate an attrition rate of 30%, leaving approximately 18 completers per arm.] If a patient drops out during Phase 2, the maximum number of consecutive abstinent days achieved in the trial will be considered as primary outcome. The inferences from analyses with missing data are considered valid provided that they are "missing at random" (Little and Rubin 1987). One can assume either parametric or semi-parametric models for missingness (Diggle and Kenward 1994; Kenward 1998; Liu et al 1999; Rotnitzky et al 1998). Inferences from various models of missingness provides a measure of the efficacy estimate from each models.

3.4.4. Significance testing and preliminary analyses: All tests for main effects will be performed at two-tailed significance $\alpha=5\%$. Before performing specific analyses (described below), we will examine all variables for outliers and normality. Demographic variables (ethnicity, gender, age) and baseline measures in the groups will be described in terms of means, standard deviations, proportions and 95% confidence intervals. The covariates (Section 3.4.1) will be included if they are found to affect outcome measures.

Hypotheses:

Primary Aim 1 [Phase 1]: The goal of primary aim 1 is to investigate the effect that both IN DDAVP and OT have on stress sensitivity. **Primary Aim 1a, hypothesis 1:** IN DDAVP will be associated with greater secretion of ACTH and subjective ratings in cocaine dependent patients compared to control patients. **Primary Aim 1b, hypothesis 2:** IN OT treatment will significantly reduce the secretion of ACTH and subjective ratings associated with IN DDAVP in cocaine dependent patients compared to control patients. The differences based on the outcomes specified in hypotheses 1 and 2 between the subjects in COC and CON groups will be examined using parametric or non-parametric matched sample test.

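### The four-sample baseline salivary cortisol profile, which the protocol's background links to failure to become abstinent, is collected before randomised dosing but enters no analysis in SAP section 3.4

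*SAP*

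**What the plan says.** **Rationale.** Protocol section 1.2 reports from a prior trial: "Cocaine-dependent patients at baseline, with an abnormal diurnal cortisol secretion profile (48% of the sample), could not become abstinent from cocaine during a lead-in". It goes on to infer that patients with similar severity of use may have quite different chances of recovery.

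**Collection.** In the protocol's Study Procedures (week 1, phase 1, item 3), at the first cocaine-negative urine, "we will collect baseline salivary cortisol samples at these approximate times: 8-9am, 11-12pm, 2-3pm, 5-6pm". Dosing comes later on both routes. For inpatients: "After baseline stress testing is completed, begin randomized administration of intranasal Oxytocin". For outpatients: "Randomized medication will begin after completion of all the physiological tests". At the end of Phase 2: "They also repeat the salivary cortisol collection, and the stress challenge with intranasal desmopressin".

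**Analysis.** The covariates in SAP 3.4.1 are "demographics, age, gender; cocaine data (TLFB, 30 days; IN vs. smoked". SAP 3.4.4 adds: "The covariates (Section 3.4.1) will be included if they are found to affect outcome measures". On randomisation, SAP 3.4.2 says: "Individuals will be stratified by route of cocaine use". Salivary or diurnal cortisol appears in no outcome, hypothesis or exploratory aim in section 3.4, and the protocol's Specific Aims do not mention it either. The SAP's only cortisol measure is a spot value at weeks 2, 4 and 6 for medical monitoring, taken on treatment. The Phase 2 primary model is a generalized linear model with a main effect of arm. The result at the end of the SAP comes from an unadjusted Wilcoxon rank-sum test.

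**The concern.** The investigators give a reason to think a baseline measure bears on outcome, and they obtain it before treatment can affect it. That makes it a legitimate candidate for adjustment. The SAP nevertheless provides no route for it: it is not a stratifier, it is not in the covariate list, and the data-driven inclusion rule cannot bring it in because that rule operates only on the 3.4.1 list. Patients give eight saliva samples (four at baseline, four at the end of Phase 2) with no analysis stated in either document.

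With 25 per arm planned and 26 patients randomised in total, a prognostic baseline factor can easily fall unevenly between arms. Adjustment is the usual way to recover precision and to remove the effect of such an imbalance from the estimate.

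**Working it through.** **Inputs from the SAP.** 25 per arm, effect size d = 0.8, two-sided 5%, power stated as at least 80% (Power Analysis, Primary aim 2). Patients randomised: 15 oxytocin, 11 placebo (Primary outcome).

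**Assumptions, not in the documents.** R², the share of outcome variance explained by the profile: 0.02, 0.05, 0.10, 0.25. Number with an abnormal profile among 50 randomised: 24 (48%), 10 (20%), 5 (10%).

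**Step 1: reproduce the planned power.** The noncentrality is d × √(n₁n₂/(n₁+n₂)) = 0.8 × √(625/50) = 0.8 × 3.536 = 2.828. The normal approximation gives power 0.807; the exact two-sample t-test (48 df) gives 0.791. The stated 80% is reproduced to within rounding of method, and the omission of cortisol does not affect it.

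For 15 and 11: 0.8 × √(165/26) = 0.8 × 2.519 = 2.015, and t-based power (24 df) is 0.490.

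**Step 2: power with the covariate.** The residual SD shrinks by √(1−R²), so the noncentrality becomes 2.828/√(1−R²) or 2.015/√(1−R²).

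| R² (assumed) | √(1−R²) | Power, 25 per arm | Power, 15 vs 11 |
|---|---|---|---|
| 0 (unadjusted) | 1.000 | 0.79 | 0.49 |
| 0.02 | 0.990 | 0.80 | 0.50 |
| 0.05 | 0.975 | 0.81 | 0.51 |
| 0.10 | 0.949 | 0.83 | 0.53 |
| 0.25 | 0.866 | 0.89 | 0.61 |

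These are normal-theory figures. The SAP names no distribution or link for the primary model, so they are approximate for a bounded count of days.

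**Step 3: cost if the covariate is useless.** With R² = 0 and two extra terms (covariate plus missing-value indicator), the degrees of freedom fall from 48 to 46 and from 24 to 22. Power stays at 0.791 with 25 per arm and goes from 0.490 to 0.487 with 15 and 11.

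**Step 4: chance imbalance.** If K of 50 patients are abnormal and 25 go to each arm, the number x in one arm is hypergeometric(50, K, 25), and the arms differ by |2x − K|. This ignores the stratification and blocking.

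| K abnormal of 50 | Chance that the arms differ by at least 4 patients |
|---|---|
| 24 | 40% |
| 10 | 29% |
| 5 | 5% |

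Four patients of 25 is 16 percentage points.

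**The case against.** **The evidence is about a different outcome.** Section 1.2 of the protocol concerns patients who could not *become* abstinent during a lead-in. The Phase 2 outcome is how long abstinence lasts *after* it has been induced, and no passage says the profile predicts that. The timing differs too: the prior profile was taken at baseline, before a lead-in, whereas here sampling waits for the first negative urine. This stands. Prognostic value in Phase 2 is an inference, and R² could be close to zero.

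**Selection at entry.** Only patients who complete abstinence induction reach Phase 2, so the abnormal share may be below 48%. This stands in part. Inpatient induction imposes abstinence, and outpatients who fail are offered it, so such patients are not necessarily screened out. A range of shares is needed.

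**A stress-based predictor analysis is already planned.** Section 1.2 ties the question of who benefits from oxytocin to the vasopressin challenge, and exploratory aim a relates the effect of oxytocin on stress sensitivity to days of abstinence. This stands. A reader might infer that the SAP ignores stress physiology as a predictor, or that a cortisol-by-arm interaction is the answer the protocol seeks. The documents support neither.

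**Bias.** A reader might also infer that the omission biases the comparison or invalidates the sample size. Randomisation protects the unadjusted comparison in expectation, its standard error already allows for chance imbalance, and the stated power reproduces.

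**The reported test cannot take a covariate.** This is true of the rank-sum test, and the power gains above do not carry over to it. The planned GLIMMIX model can take one.

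**The text is an excerpt.** The SAP begins mid-list, so absence from its assessment lists proves little. Section 3.4 itself is present, and the point rests on that section.

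**Conclusion.** The point holds as a cheap improvement rather than an error in the plan. A baseline measure for which the protocol gives a rationale is collected before dosing and used in no analysis in SAP 3.4, and the plan's own covariate rule cannot admit it.

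The benefit is uncertain. It ranges from nothing, if the profile does not predict maintenance of abstinence, to about 10 points of power with 25 per arm (0.79 to 0.89) if R² were 0.25, a value that no document supports. At the sample actually randomised, power at d = 0.8 stays at or below 0.61 over the whole assumed range, so adjustment would not rescue that comparison. The chance of a difference of at least four abnormal-profile patients between arms of 25 is 40% if the share is 48%, but 5% if it is 10%.

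**What to change.** - **Covariate.** Add one baseline diurnal cortisol summary to SAP 3.4.1. It should use all four samples (for example the slope fitted over the sampling times) and be defined before the cortisol data are seen by arm. Neither document defines an abnormal profile, and a continuous summary avoids choosing a cut-point.
- **Model.** Enter it in the Phase 2 GLIMMIX model regardless of significance, exempt from the inclusion rule in 3.4.4, with a stated rule for missing values.
- **Interaction.** Treat cortisol by arm as exploratory only, alongside exploratory aim a.
- **Reporting.** Tabulate the baseline profile by arm. Since the SAP already reports an unadjusted rank-sum result, label any adjusted analysis done now as a post hoc sensitivity analysis.
- **End-of-Phase-2 samples.** State what the repeat collection is for.

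The cost is SAP wording and one or two degrees of freedom, with no new procedures or samples. The downside is possibly little or no gain in precision.

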#### Number of completers required to accomplish study aims

50

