#### Projected number of subjects who will be enrolled to obtain required number of completers

75

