**Create or insert table to describe the exclusion criteria and methods to ascertain them**

EXCLUSION CRITERIA	METHOD OF ASCERTAINMENT
1. Meets DSM IV criteria for bipolar disorder, schizophrenia or any psychotic disorder other than transient psychosis due to drug abuse. Substance Induced Mood Disorder with Hamilton Depression Scale score $\geq 15$ will be excluded. Patients with Major Depressive Disorder will be eligible to participate, provided they are in remission (Hamilton Depression Scale-25 Score < 8), whether receiving treatment or not.	MINI interview, self-report
2. History of allergic, dermatological, or adverse event related to oxytocin or desmopressin. Patient using oxytocin or vasopressin-based products cannot participate.	Self report
3. Chronic organic mental disorder, insufficient proficiency in English, or any condition or status (illiteracy) that would render an individual incapable of giving informed consent.	Psychiatric evaluation
4. Significant current suicidal risks, suicide attempt within the past year.	Psychiatric evaluation
5. Unstable physical disorders, which might make participation hazardous: hypertension (>140/90), hepatitis (patients with chronic	Medical evaluation

mildly elevated transaminase levels (2-3 X upper limit of normal will be considered acceptable if PT/PTT is normal), serum sodium (Na) < 133 mEq/L, renal failure (creat >2; BUN > 40. History of hyponatremia. Patients on medication (\*) (see partial list below) that may induce hyponatremia will not be excluded, provided no evidence of hyponatremia is found at screening.

6. Coronary vascular disease as indicated by history, or suspected by abnormal ECG. Electrocardiogram, medical history

7. Currently meets DSM-IV criteria for another substance dependence or abuse disorder other than nicotine, or alcohol. If alcohol dependent, must not be in need of detoxification. MINI, medical eval, utox

8. Participants who cannot comply with study procedures during the inpatient or outpatient abstinence induction (phase 1) will not proceed to phase 2. Study performance

9. Pregnancy, positive urine pregnancy test, or breastfeeding. Women who wish to participate must agree to use a method of contraception during the study and sign a written commitment to that effect, and submit to a urine pregnancy test every two weeks of phase 2 History, medical monitoring.

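### The SAP enrols 50 cocaine-dependent patients and randomises all 50, while the protocol projects 75 enrolled to reach 50 and screens patients out before Phase 2; the Phase 2 power figure has no slack for that loss

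*SAP*

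**What the plan says.** **SAP.** Section 3.4.2 opens with "In PHASE 1, we will enroll a total of 100 participants", made up of 50 cocaine-dependent patients and 50 matched controls. It continues: "In PHASE 2, we will randomize the 50 COC patients into two groups", with 25 to oxytocin and 25 to placebo. Section 3.4.3 uses the same 25 per arm for the Phase 2 intent-to-treat set. It expects little attrition in Phase 1, with no figure, and 30% in Phase 2, "leaving approximately 18 completers per arm". The Power Analysis paragraph claims at least 80% power with 25 per arm, two-sided 5%, for an effect size of 0.8 or more.

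**Protocol.** Under Description of Subject Population, Sample #1 (cocaine-dependent), the entry for "Number of completers required to accomplish study aims" is 50. The entry for "Projected number of subjects who will be enrolled to obtain required number of completers" is 75. Sample #2 (controls) carries the same two figures.

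The protocol also describes a step between enrolment and Phase 2:
- Exclusion criterion 8 for the cocaine-dependent sample reads: "Participants who cannot comply with study procedures during the inpatient or outpatient abstinence induction (phase 1) will not proceed to phase 2".
- The Design Overview and the outpatient version of Phase 1 add the abstinence rule. A patient who does not reach abstinence in two outpatient attempts must go through inpatient induction, and one who cannot do that is referred elsewhere.
- In the outpatient version, randomised medication starts only after the physiological tests are complete.

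**The concern.** The two documents give different enrolment figures for the same sample, and the SAP's figure leaves out a step that the protocol describes. In the SAP, the number enrolled, the number randomised and the number behind the power statement are all 50. In the protocol, some enrolled patients may not reach randomised treatment, and the projection of 75 looks like an allowance for loss that the SAP never mentions.

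The SAP's remark on low Phase 1 attrition does not close the gap. The reason it offers is that two days of testing yield usable Phase 1 data. That says nothing about how many patients get through induction to be randomised.

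What is at stake is the basis of the Phase 2 power statement. Someone working from the SAP alone would stop enrolling at 50 and treat 25 per arm as assured.

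**Working it through.** **Inputs.** Effect size d = 0.8, two-sided 5% and 25 per arm (SAP, Power Analysis); 50 enrolled (SAP 3.4.2); 75 enrolled for 50 completers (protocol, Sample #1). The share lost before randomisation is not given in either document, so it is varied as an assumption. The SAP names no test for its power figure; a comparison of two means is assumed.

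**Step 1: reproduce the plan's figure.** By the normal approximation, with n per arm, power = Φ(d·√(n/2) − 1.96).

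For n = 25: 0.8 × √12.5 = 2.828; 2.828 − 1.96 = 0.868; Φ(0.868) = 80.7%.

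The two-sample t-test (noncentral t) gives 79.1%. The stated figure is therefore reproduced, with nothing to spare.

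**Step 2: the slack at 25 per arm.** For n = 24: 0.8 × √12 = 2.771; 2.771 − 1.96 = 0.811; Φ(0.811) = 79.1% (t-test 77.4%). Randomising 48 instead of 50 already puts power below 80% by either method.

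**Step 3: carry each enrolment figure through an assumed loss.** Number randomised = enrolled × (1 − loss), split equally, with everyone who passes induction randomised.

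| Loss before randomisation (assumed) | 50 enrolled: per arm | Power, normal / t | 75 enrolled: per arm | Power, normal / t |
|---|---|---|---|---|
| 0% | 25 | 80.7% / 79.1% | 37.5 | 93.4% / 92.8% |
| 10% | 22.5 | 76.5% / 74.6% | 33.8 | 90.8% / 89.9% |
| 20% | 20 | 71.6% / 69.3% | 30 | 87.3% / 86.1% |
| 33.3% | 16.7 | 63.7% / 61.0% | 25 | 80.7% / 79.1% |

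**Step 4: break-even.** With 75 enrolled, 50 are randomised when loss = 1 − 50/75 = 33.3%. With 50 enrolled, 50 are randomised only when loss = 0.

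**Step 5: enrolment needed to randomise 50.** 50 / (1 − loss), rounded up: 56 at 10%, 63 at 20%, 75 at 33.3%.

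The 30% Phase 2 attrition is not applied anywhere above. Section 3.4.3 gives dropouts an outcome value (their longest abstinent run while in the trial), so they stay in the analysis.

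**The case against.** The best defence is that the protocol already holds the missing allowance. If 75 are enrolled, 25 per arm survives any loss up to one third. The inpatient route, which the protocol's section on delay to treatment describes as guaranteeing abstinence, makes a loss of that size less likely. Nothing in the power calculation is wrong. This stands, and it limits the point to a conflict between the two documents. It does not remove the conflict, because the SAP text available never mentions 75 and states that 50 are enrolled. That text is an extract which refers to a section 3.1.1 that is not in it, so the omission can be asserted only for the sections we have.

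Four stronger readings are tempting and are not supported:

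- **The plan cannot deliver 25 per arm.** This follows only from enrolling 50 with some loss. The protocol's 75 delivers 25 per arm unless more than a third are lost.
- **Induction failure should be put at 48%.** Protocol background section 1.2 speaks of patients who "could not become abstinent from cocaine during a lead-in of a clinical trial". The 48% beside it is the share of that sample with an abnormal cortisol profile. The overall failure rate in that trial is not given, so 48% is neither an estimate nor a bound for this one.
- **The intent-to-treat set is wrongly defined.** Section 3.4.3 already defines it as all subjects randomised; the 25 per arm in parentheses is the planned count.
- **The SAP's 18 or so completers per arm falls short of the protocol's 50.** This takes completers to mean patients who finish Phase 2. The protocol does not say so, and controls, who take part only in Phase 1, carry the same 50 and 75. That favours reading the term as Phase 1 completers.

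A reader might also see confirmation in the 26 patients reported as randomised at the end of the SAP. That is a result, and no reason for the shortfall is given. It says nothing about what the plan assumed.

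**Conclusion.** The point holds as a contradiction between the documents on a figure that the Phase 2 power statement relies on. The SAP's enrolment of 50 supports 25 per arm only with zero loss before randomisation, and the protocol provides for such loss. Because 25 per arm sits at the 80% threshold, even two patients lost from 50 takes power below it. The assumed 10% and 20% losses cost about 4 and 9 percentage points by the normal approximation (80.7% to 76.5% and 71.6%). On the protocol's 75, the same losses leave power at 86% or more by either method.

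This rests on d = 0.8 and a two-means comparison, both taken as the plan's own basis, and on assumed loss rates. It does not show that the trial as planned was underpowered. It shows that the reader cannot tell which enrolment figure applies, or how much loss the plan allows for.

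**What to change.** Reconcile the two figures in SAP section 3.4.2. State enrolment of cocaine-dependent patients (the protocol's 75) separately from the number to be randomised (50, 25 per arm), and say that the difference allows for patients who do not pass from Phase 1 to randomisation.

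In the Power Analysis paragraph, state Phase 2 power as conditional on the number actually randomised, and show it over an assumed range of pre-randomisation loss, as in the table above.

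The change is one of wording, with no extra patients beyond those the protocol already projects, and no induction or eligibility rule is touched. The drawback is that the stated power may look slightly less favourable than a flat claim of at least 80%.
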